#### Secondary Objectives

A similar statistical approach as for the primary objective will be used considering the rSBA antibody titers for Nimenrix® and hSBA antibody titers for NeisVac-C®.

[figure not shown]
The testing approach will be done in parallel and using a step by step approach for the 2 comparators:

#### Nimenrix®:

If the non-inferiority using seroprotection rates of MenACYW conjugate vaccine against Nimenrix® measured by rSBA is demonstrated then the non-inferiority using rSBA GMTs will be tested. If the non-inferiority using rSBA GMTs of MenACYW conjugate vaccine against Nimenrix® is demonstrated then the superiority using rSBA GMTs will be tested.

#### Neis Vac- $C^{\mathbb{R}}$ :

If the non-inferiority using seroprotection rates of MenACYW conjugate vaccine against NeisVac-C® measured by hSBA is demonstrated then the non-inferiority using hSBA GMTs will be tested. And if the non-inferiority using hSBA GMTs is demonstrated then the superiority using hSBA GMTs will be tested.

To conclude, non-inferiority using seroprotection rates of MenACYW conjugate vaccine against Nimenrix® measured by rSBA or non-inferiority using seroprotection rates of MenACYW conjugate vaccine against NeisVac-C® measured by hSBA have to be demonstrated.

#### **Observational Objectives**

For immunogenicity and safety observational objectives, the descriptive analyses will be done according to each vaccine group. The main parameters will be described with 95% CI using the exact binomial distribution (Clopper-Pearson method) for proportions and using the normal approximation of the Log10 concentrations/titers, followed by a back transformation for GMTs.

#### Calculation of Sample Size:

To complete the primary objective a total of 675 subjects were initially planned to be enrolled according to a ratio 1:1:1 (MenACYW: Nimenrix®: NeisVac-C®). This sample size will provide acceptable global powers considering an overall one-sided alpha of 2.5% (ie, 1.25% adjusted alpha for each of the 2 main non-inferiority tested, then same level of alpha is used for the subsequent tests as a ranking testing strategy is used), an initial drop-out rate of 10% (ie, 202 evaluable subjects per group; not taking into account the impact of COVID-19) and based on the following additional hypotheses:

Objective number	Step	Comparator	Statistical test	Endpoint	Ref. MenACYW vs Comparator	Clinical margin	Standard deviation (SD)	Indivi- dual power	Sequential power
1	1	Nimenrix hSBA	NI	Seroprote ction rates	98% vs 88%	10%		>99.9%	>99.9%
	2	Nimenrix hSBA	NI	GMTs	GMTR=1.5	1.5	0.5	>99.9%	>99.9%
	3	Nimenrix hSBA	Sup	GMTs	GMTR=1.5	-	0.5	90.1%	89.9%
	4	Nimenrix hSBA	Sup	Seroprote ction rates	98% vs 88%	10%		95.8%	86.1%
2	1	Neisvac-C rSBA	NI	Seroprote ction rates	98% vs 98%	10%		>99.9%	>99.9%
	2	Neisvac-C rSBA	NI	GMTs	GMTR=1	1.5	0.5	90.1%	90.1%
	3	Neisvac-C rSBA	Sup	GMTs	GMTR=1.5	-	0.5	90.1%	81.2%

NI: non-inferiority; Sup: superiority

GMTR: Geometric Mean of Titers ratios of MenACYW vs Comparator

One-sided Alpha of 1.25% used for all calculations

Sequential power correspond to the overall power of each step of the statistical tests to be performed

Reference seroresponse rates and SDs made from Phase II and III toddler studies MET51, MET32 and MET54.

In addition, considering such sample size will also provide acceptable global powers to achieve the secondary objective, considering an overall one-sided alpha of 2.5% (ie, 1.25% adjusted alpha for each of the 2 main non-inferiority tested, then same level of alpha is used for the subsequent tests as a ranking testing strategy is used), an initial drop-out rate of 10% (not taking into account the impact of COVID-19), and based on the following additional hypotheses:

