#### Superiority

If the non-inferiority testing succeeds then a superiority approach will be used to compare post-vaccination (ie, 30 days after the vaccination) seroprotection rates and/or GMTs of MenACYW conjugate vaccine to that of Nimenrix® and NeisVac-C®, using a two-sided 95% CI with the following hypotheses:

For seroprotection rates

 $H_0: \pi_{\text{MenACYW}} - \pi_{\text{Comparator}} \leq 0$ 

 $H_1: \pi_{\text{MenACYW}} - \pi_{comparator} > 0$ 

Or

For GMTs

 $H_0: GMT_{MenACYW}/GMT_{Comparator} \leq 1$ 

 $H_1: GMT_{MenACYW}/GMT_{Comparator} > 1$ 

with:

- Comparator: Nimenrix® or NeisVac-C®
- $\pi$ : seroprotection rates

For the seroprotection rates, the 95% CI of the difference in proportions will be computed using the Wilson Score method without continuity correction (Newcombe method).

For the GMTs, the two-sided 95% CI of the ratio of post-vaccination GMTs will be calculated using normal approximation of log-transformed titers.

The non-inferiority will be demonstrated against seroprotection rates if the null hypothesis is rejected, ie, if the lower limit of the two-sided 95% CI for the difference between the seroprotection rates is > -10%.

The non-inferiority will be demonstrated against GMTs if the null hypothesis is rejected, ie, lower limit of the two-sided 95% CI for the ratio of GMTs > 1/1.5.

The superiority will be demonstrated against seroprotection rates if the null hypothesis is rejected, ie, if the lower limit of the two-sided 95% CI for the difference between the seroprotection rates is > 0%.

The superiority will be demonstrated against GMTs if the null hypothesis is rejected, ie, lower limit of the two-sided 95% CI for the ratio of GMTs > 1.

[figure not shown]
The testing approach will be done in parallel and using a step by step approach for the 2 comparators:

Nimenrix®:

If the non-inferiority using seroprotection rates of MenACYW conjugate vaccine against Nimenrix® measured by hSBA is demonstrated then the non-inferiority using hSBA GMTs will be tested. If the non-inferiority using hSBA GMTs of MenACYW conjugate vaccine against Nimenrix® is demonstrated then the superiority using hSBA GMTs will be tested. If the superiority using hSBA GMTs is demonstrated then the superiority using hSBA seroprotection rates will be tested.

Neis Vac- $C^{\mathbb{R}}$ :

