#### Antibody Responses (hSBA GMTs) at D30

Toddlers who either were meningococcal vaccine naïve or had received monovalent MenC vaccination during infancy

The GMTRs (stratified on priming vaccination background) were 7.59, 1.28, and 1.32 for serogroups C, Y and W, respectively, with the lower bound of the 95% CI greater than 1.0; and the GMTR (stratified on priming vaccination background) was 0.819 for serogroup A, with the upper bound of the 95% CI lower than 1.0.

Meningococcal vaccine-naïve toddlers

The GMTRs were 1.03 and 1.18 (with the lower bound of the 95% CI below 1.0) for serogroups A and Y, respectively, and 16.5 and 1.34 (with the lower bound of the 95% CI greater than 1.0) for serogroups C and W, respectively.

Toddlers who received monovalent MenC vaccination during infancy

The GMTRs were 0.496 (with the upper bound of the 95% CI lower than 1.0) for serogroup A, 1.34 and 1.29 (with the lower bound of the 95% CI below 1.0) for serogroups C and W, respectively, and 1.53 (with the lower bound of the 95% CI greater than 1.0) for serogroup Y.

Antibody Responses (rSBA GMTs and seroresponse Titers ≥1:8 seroresponse) at D30

Toddlers who either were meningococcal vaccine naïve or had received monovalent MenC vaccination during infancy

At D30, meningococcal rSBA GMTs were lower in MenACYW-recipients than in Nimenrix®-recipients for serogroup A (1382 and 4882, respectively), and higher in MenACYW-recipients than in Nimenrix®-recipients for serogroup C (2150 and 686, respectively).

Thirty days after vaccination, the percentages of subjects with rSBA antibody titers  $\geq 1:8$  were high and comparable between MenACYW- and Nimenrix®-recipients ranging from 97.3% to 100.0%.

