## 2 Study Objectives

### 2.1 Primary Objectives

- 1) To demonstrate the non-inferiority of the seroprotection rate (antibody titers ≥ 1:8) to meningococcal serogroup C following the administration of a single dose of MenACYW conjugate vaccine or Nimenrix® as measured by hSBA. If the non-inferiority of the seroprotection rate (antibody titers ≥ 1:8) is demonstrated, then
  - 1.1) to demonstrate the non-inferiority of the antibody response (geometric mean titers [GMT]) to meningococcal serogroup C following the administration of a single dose of MenACYW conjugate vaccine or Nimenrix® as measured by hSBA. If the non-inferiority of the antibody response (GMT) is demonstrated, then
  - 1.2) to demonstrate the superiority of the antibody response (GMT) to meningococcal serogroup C following the administration of a single dose of MenACYW conjugate vaccine or Nimenrix® as measured by hSBA. If the superiority of the antibody response (GMT) is demonstrated, then
  - 1.3) to demonstrate the superiority of the seroprotection rate to meningococcal serogroup C following the administration of a single dose of MenACYW conjugate vaccine or Nimenrix® as measured by hSBA.
- 2) To demonstrate the non-inferiority of the seroprotection rate (antibody titers ≥ 1:8) to meningococcal serogroup C following the administration of a single dose of MenACYW conjugate vaccine or NeisVac-C® as measured by rSBA. If the non-inferiority of the seroprotection rate is demonstrated, then
  - 2.1) to demonstrate the non-inferiority of the antibody response (GMT) to meningococcal serogroup C following the administration of a single dose of MenACYW conjugate vaccine or NeisVac-C® as measured by rSBA. If the non-inferiority of the antibody response (GMT) is demonstrated, then
  - 2.2) to demonstrate the superiority of the antibody response (GMT) to meningococcal serogroup C following the administration of a single dose of MenACYW conjugate vaccine or NeisVac-C® as measured by rSBA.

The endpoints for the primary objectives are presented in Section 9.1.

Overall, the primary objective for the study will be met if, objective 1) - non-inferiority of the seroprotection rate versus Nimenrix $^{\mathbb{B}}$  as measured by hSBA, or objective 2) - non-inferiority of the seroprotection rate versus NeisVac-C $^{\mathbb{B}}$  as measured by rSBA, is met.

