# 5.3 Modification of the Study and Protocol

Any amendments to this study plan and protocol must be discussed with and approved by the Sponsor. If agreement is reached concerning the need for an amendment, it will be produced in writing by the Sponsor, and the amended version of the protocol will replace the earlier version. All substantial amendments (e.g., those that affect the conduct of the study or the safety of subjects) require IEC / IRB approval, and must also be forwarded to regulatory authorities.

An administrative / non-substantial amendment to a protocol is one that modifies some administrative, logistical, or other aspect of the study but does not affect its scientific quality or have an impact on the subjects' safety. In case of non-substantial amendment, IECs / IRBs have to be notified.

The Investigator is responsible for ensuring that changes to an approved study, during the period for which IEC / IRB approval has already been given, are not initiated without IEC / IRB review and approval, except to eliminate apparent immediate hazards to subjects.

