# **6.4** Blinding and Code-breaking Procedures

The MEQ00065 study is modified double-blind, which means that both the subject and the Investigator remain unaware of the treatment assignments throughout the study. An unblinded vaccine administrator will administer the appropriate vaccine but will not be involved in safety data collection. The Sponsor and laboratory personnel performing the serology testing will also remain blinded to treatment assignments throughout the study until database lock.

The code may be broken in the event of an AE only when the identification of the vaccine received could influence the treatment of the subject. Code-breaking should be limited to the subject(s) experiencing the AE.

The blind can be broken by the Investigator or a delegate through the IRT system, as explained in the code-breaking procedures described in the Operating Guidelines. Once the emergency has been addressed by the site, the Investigator or a delegate must notify the Sanofi Pasteur RMO if a subject's code was broken. All contact attempts with the Sponsor prior to unblinding are to be documented in the source documents, and the code-breaking CRF is to be completed.

A request for the code to be broken may also be made: by the GPV Department through an internal system for reporting to health authorities in the case of an SAE as described in ICH E2Aa. In this case, the code will be broken only for the subject(s) in question. The information resulting from code-breaking (ie, the subject's vaccine or group assignment) will not be communicated to either the Investigator or the immediate team working on the study, except for the GPV representative.

-

<sup>a All unexpected and related SAEs submitted to European Union competent authorities must be unblinded.

The IEC/IRB must be notified of the code-breaking. All documentation pertaining to the event must be retained in the site's study records and in the Sanofi Pasteur files. Any intentional or unintentional code-breaking must be reported, documented, and explained, and the name of the person who requested it must be provided to the Sponsor.

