# **Superiority**

If the non-inferiority testing succeeds then a superiority approach will be used to compare post-vaccination (ie, 30 days after the vaccination) seroprotection rates and/or GMTs of MenACYW conjugate vaccine to that of Nimenrix® and NeisVac-C®, using a two-sided 97.5% CI with the following hypotheses:

For seroprotection rates

$$H_0: \pi_{\text{MenACYW}} - \pi_{\textit{Comparator}} \leq 0$$

$$H_1: \pi_{\text{MenACYW}} - \pi_{\textit{Comparator}} > 0$$

Or

For GMTs

$$H_0: GMT_{\text{MenACYW}} / GMT_{comparator} \le 1$$

$$H_1: GMT_{MenACYW}/GMT_{Comparator} > 1$$

with:

- Comparator: Nimenrix® or NeisVac-C®
- $\pi$ : seroprotection rates

For the seroprotection rates, the 97.5% CI of the difference in proportions will be computed using the Wilson Score method without continuity correction (Newcombe method).

For the GMTs, the two-sided 97.5% CI of the ratio of post-vaccination GMTs will be calculated using normal approximation of log-transformed titers.

The non-inferiority will be demonstrated against seroprotection rates if the null hypothesis is rejected, ie, if the lower limit of the two-sided 97.5% CI for the difference between the seroprotection rates is > -10%.

The non-inferiority will be demonstrated against GMTs if the null hypothesis is rejected, ie, lower limit of the two-sided 97.5% CI for the ratio of GMTs > 1/1.5.

The superiority will be demonstrated against seroprotection rates if the null hypothesis is rejected, ie, if the lower limit of the two-sided 97.5% CI for the difference between the seroprotection rates is > 0%.

The superiority will be demonstrated against GMTs if the null hypothesis is rejected, ie, lower limit of the two-sided 97.5% CI for the ratio of GMTs > 1.

The testing approach will be done in parallel and using a step by step approach for the 2 comparators (3 steps):

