# 5.6 Data Review for Statistical Purposes

A review of the data has been anticipated through the data review process led by data management before database lock. This review of the data included a statistical review.

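### The Protocol Synopsis tests the primary steps with 95% CIs where the rest of the plan requires 97.5%; separately, passing on the alpha of a completed chain is an optional gain, not a correction

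*Protocol*

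**What the plan says.** The Synopsis (Calculation of Sample Size) and SAP 5.5 set an overall one-sided alpha of 2.5% for the primary family and divide it: "1.25% adjusted alpha for each of the 2 main non-inferiority tested, then same level of alpha is used for the subsequent tests". The Nimenrix chain has four steps on hSBA: seroprotection non-inferiority, GMT non-inferiority, GMT superiority, seroprotection superiority. The NeisVac-C chain has three on rSBA: seroprotection non-inferiority, GMT non-inferiority, GMT superiority. They run in parallel, and no visible text links the alpha of one to the outcome of the other.

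Protocol 12.1.1.2 gives the GMT non-inferiority criterion as "lower limit of the two-sided 97.5% CI for the ratio of GMTs > 1/1.5"; SAP 5.1.1.2 has the same limit, and both use 97.5% for every other step. The Synopsis (Statistical Methods, Superiority) gives the same criterion as "lower limit of the two-sided 95% CI for the ratio of GMTs > 1/1.5", and uses 95% for every other step as well.

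Protocol 2.1 defines overall success on seroprotection alone: "Overall, the primary objective for the study will be met if, objective 1) - non-inferiority of the seroprotection rate versus" Nimenrix by hSBA, or the same versus NeisVac-C by rSBA.

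**The concern.** Two things follow from setting these passages side by side.

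First, the Synopsis contradicts itself and the body. A two-sided 95% CI is a one-sided 2.5% test. With two chains and a claim available from either, 2.5% per chain is not 2.5% overall, so the stated error control fails if the Synopsis rule is applied. The Synopsis secondary analyses follow the same approach and inherit the conflict, whereas SAP 5.1.2.2 uses 97.5%.

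Second, under the 97.5% rule nothing says what happens to a chain's 1.25% once all its steps are rejected. It lapses while the other chain stays at 1.25%. The step with most to gain is NeisVac-C GMT non-inferiority (objective 2.1), planned at 90.1%. Protocol 1.4 says no licensed ACWY vaccine has shown MenC non-inferiority to NeisVac-C. That section does not single out GMTs, but GMT is the NeisVac-C non-inferiority step with the lower planned power.

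**Working it through.** **Inputs** (Synopsis sample size table; SAP Table 5.2): 202 evaluable per arm; SD 0.5 on log10 titres; GMT margin 1.5; NeisVac-C GMTR 1 for non-inferiority; Nimenrix GMTR 1.5; Nimenrix-chain seroprotection 98% vs 88%; one-sided 1.25%.

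**Reproducing the plan.** The noncentrality is log10(1.5) / (0.5 × √(2/202)) = 0.1761 / 0.04975 = 3.54. With 402 df the noncentral t gives 90.1% at one-sided 1.25%, the plan's figure, and 94.2% at 2.5%. The plan's Nimenrix chain is 0.899 × 0.958 = 86.1%, as stated. With the Newcombe interval that the plan specifies, step 4 has 97.2% power rather than 95.8%, so the chain completes with probability 0.901 × 0.972 = 87.6%.

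**Synopsis rule.** If the GMT non-inferiority null is true in both chains and the chains were independent, testing each at 2.5% gives 1 − 0.975² = 4.94%. The shared MenACYW arm lowers this somewhat. A simulation of both chains (400,000 runs per scenario, hSBA/rSBA correlation 0 to 1, Monte Carlo SE at most 0.035 points) gives 4.57-4.99%. The 97.5% rule gives 2.38-2.48%.

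**Transfer: error control.** If both chains contain a true null, alpha can move only after a true null has already been rejected at 1.25%, so the familywise error is the same as under the fixed split. If only one chain contains a true null, it is tested at no more than 2.5%. The simulation agrees:
- NeisVac-C GMTR at 1/1.5 with an effective Nimenrix chain: false non-inferiority 2.38-2.46%.
- NeisVac-C GMTR 1 with Nimenrix GMTR 16.5: false superiority 2.46-2.50%.

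**Transfer: power.** Under independence, power = p(1.25%) + [p(2.5%) − p(1.25%)] × C, where C is the probability that the Nimenrix chain completes. With the plan's C: 0.901 + 0.041 × 0.861 = 93.6%. Simulating both chains in full gives 93.7% at hSBA/rSBA correlation 0 and 93.1% at correlation 1. The documents do not give this correlation, so the whole range is shown.

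| True NeisVac-C GMTR | Fixed split | With transfer |
|---|---|---|
| 0.90 | 64.4% | 73.0-73.1% |
| 0.95 | 80.0% | 85.5-86.1% |
| 1.00 (planned) | 90.1% | 93.1-93.7% |
| 1.05 | 95.7% | 97.0-97.5% |
| 1.10 | 98.3% | 98.8-99.1% |

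The documents do not favour a GMTR below 1 over one above 1. NeisVac-C GMT superiority at the planned GMTR of 1.5 also goes from 90.1% to 93.1-93.7%. With a fixed split, power of 93.1-93.7% would take 225-231 evaluable per arm, which is 23-29 more than 202.

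**Dependence on the Nimenrix rate.** Alpha is freed only after seroprotection superiority over Nimenrix. With MenACYW at 98%, Nimenrix GMTR 1.5, NeisVac-C GMTR 1 and independence:

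| Nimenrix rate | C | NeisVac-C GMT non-inferiority power |
|---|---|---|
| 88% (planned) | 87.6% | 0.901 + 0.041 × 0.876 = 93.7% |
| 90% | 80.5% | 93.4% |
| 92% | 63.0% | 92.7% |
| 94% | 34.5% | 91.5% |

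**The case against.** **On the optional part**, the case for leaving the plan alone is respectable. A fixed split with parallel sequences is a standard valid choice, the plan claims only acceptable power, and 90.1% is acceptable. The fixed split keeps the NeisVac-C result independent of whether Nimenrix superiority is shown. Uniform 97.5% CIs give at least 95% simultaneous coverage for one chosen comparison per chain; 95% CIs used after transfer do not. All of this stands, and it is why the change is optional.

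The size of the gain is also conditional. MET54 found 77/86 = 89.5% for Nimenrix (Protocol 1.2.1.1), which supports the planned rate as a point estimate, but its Wilson 95% interval runs from about 81% to 94%. The planned inputs are also not one coherent normal titre distribution. With SD 0.5, a GMTR of 1.5 and 98% for MenACYW would put Nimenrix near 95.6%, while 98% vs 88% would need a GMTR near 2.75. The simulation drew rates independently of titres, so its two-figure range is tied to the plan's own pair of inputs. MET51 points to a large titre difference in vaccine-naive toddlers ("16.5 and 1.34 (with the lower bound of the 95% CI greater than 1.0) for serogroups C and W, respectively"), and with GMTR 16.5 the power with transfer is 94.0-94.1% at the planned rates. That does not remove the dependence on the rate gap.

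**Stronger readings.** A reader might infer that the trial will be analysed at twice its stated alpha. The documents do not support that: Protocol 12.1.1.2, the SAP and the power calculations all use 1.25% per chain, and only the Synopsis limits depart from it. A reader might also infer that the missing transfer rule is an error, or that it endangers the primary objective. Neither holds. The split controls the error rate, and overall success rests on two seroprotection steps that each have over 99.9% power already.

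**Conclusion.** The Synopsis is wrong as written. Its 95% decision limits conflict with its own 1.25% per chain, with Protocol 12.1.1.2 and with the SAP. Taken literally they allow about 4.6-5.0% familywise error in place of 2.5%.

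The absence of alpha transfer is a missed efficiency, not a fault. At the planned inputs, transfer adds about 3.0 to 3.6 points to NeisVac-C GMT non-inferiority (90.1% to 93.1-93.7%), without extra subjects, and it can never reject less than the present rule. This rests on 202 evaluable per arm, SD 0.5, Nimenrix GMTR 1.5, rates of 98% vs 88%, and an unknown hSBA/rSBA correlation between 0 and 1. The gain falls to about 1.4 points if the Nimenrix rate is 94%. It also presupposes the 97.5% rule, because under the Synopsis limits no alpha is left to pass on.

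**What to change.** **Required.** In the Synopsis, change the confidence level and every non-inferiority and superiority decision limit for the primary objectives from 95% to 97.5%, and state that the secondary objectives follow the same level. Leave the 95% CIs for the observational analyses as they are. This aligns the Synopsis with the rule already in the body and the SAP, and costs only a documented correction under Protocol 5.3.

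**Optional.** Add to Protocol 12.1.1.2 and SAP 5.1.1, for the primary family only: *If every step of one primary chain is rejected at one-sided 1.25%, that alpha passes to the other chain, whose steps are then tested in the same order with two-sided 95% CIs.* Tabulate both the 97.5% and the 95% CIs. The costs are a more complex rule, the loss of simultaneous coverage noted above, and probably a substantial amendment: "All substantial amendments (e.g., those that affect the conduct of the study or the safety of subjects) require IEC / IRB approval".

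Timing decides whether the option is open. Under Protocol 6.4 the sponsor and the serology laboratory staff "remain blinded to treatment assignments throughout the study until database lock", so the change is clean only before that point. SAP 5.6 already describes the pre-lock review in the past tense ("This review of the data included a statistical review"), so the window may be short or closed. If the database has been locked or unblinded, leave the testing rule unchanged and correct only the Synopsis.

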#### Non-Inferiority

A non-inferiority testing approach will be used to compare post-vaccination (ie, 30 days after the vaccination) seroprotection rates and GMTs of MenACYW conjugate vaccine to that of Nimenrix® and NeisVac-C®, using a two-sided 95% Confidence Interval (CI) with the following hypotheses:

For seroprotection rates:

$$H_0: \pi_{\text{MenACYW}} - \pi_{\textit{Comparator}} \leq -0.1$$

$$H_1: \pi_{\text{MenACYW}} - \pi_{\textit{Comparator}} > -0.1$$

Or

For GMTs

$$H_0: GMT_{MenACYW}/GMT_{Comparator} \leq 1/\delta$$

$$H_1: GMT_{MenACYW}/GMT_{Comparator} > 1/\delta$$

with:

- Comparator: Nimenrix® or NeisVac-C®
- $\pi$ : seroprotection rates
- δ: non-inferiority margin set at 1.5

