#### **5.1.1.2** Statistical Methods

For the seroprotection rates, the 97.5% CI of the difference in proportions will be computed using the Wilson Score method without continuity correction (Newcombe method).

For the GMTs, the two-sided 97.5% CI of the ratio of post-vaccination GMTs will be calculated first using normal approximation of log-transformed titers and then by taking the antilogarithms of the lower and upper limits of the provided 97.5% CI.

The non-inferiority will be demonstrated against seroprotection rates if the null hypothesis is rejected, i.e., if the lower limit of the two-sided 97.5% CI for the difference between the seroprotection rates is > -10%.

The non-inferiority will be demonstrated against GMTs if the null hypothesis is rejected, i.e., lower limit of the two-sided 97.5% CI for the ratio of GMTs > 1/1.5.

The superiority will be demonstrated against seroprotection rates if the null hypothesis is rejected, i.e., if the lower limit of the two-sided 97.5% CI for the difference between the seroprotection rates is > 0%.

The superiority will be demonstrated against GMTs if the null hypothesis is rejected, i.e., lower limit of the two-sided 97.5% CI for the ratio of GMTs > 1.

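### Nimenrix hSBA chain: the stated 95.8% and 86.1% are not the powers of the planned tests, and both are slightly too low (97.2% and about 89%)

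*Protocol*

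**What the plan says.** The primary-objective power tables are in the protocol synopsis (Calculation of Sample Size) and in SAP section 5.5, Table 5.2. Both give four steps for MenACYW against Nimenrix by hSBA:

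- Step 1, non-inferiority of seroprotection rates, 98% vs 88%: power above 99.9%.
- Step 2, non-inferiority of GMTs, GMT ratio 1.5, SD 0.5: above 99.9%.
- Step 3, superiority of GMTs. The row reads "GMTR=1.5 - 0.5 90.1% 89.9", so individual power is 90.1% and sequential power 89.9%.
- Step 4, superiority of seroprotection rates, 98% vs 88%: individual 95.8%, sequential 86.1%.

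The protocol notes under the table say "One-sided Alpha of 1.25% used for all calculations" and "Sequential power correspond to the overall power of each step of the statistical tests to be performed". The sample-size text assumes "an initial drop-out rate of 10% (ie, 202 evaluable subjects per group".

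For the analysis, SAP 5.1.1.2 and Protocol 12.1.1.2 specify a 97.5% interval for the rate difference, "computed using the Wilson Score method without continuity correction (Newcombe method". For the GMT ratio they specify a 97.5% interval by normal approximation on log titers. Neither document says how step powers were combined into sequential power, or which joint distribution of titers links the rates to the GMT ratio.

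**The concern.** Two things looked wrong. First, the step-4 power does not match the interval that will decide step 4. Second, 86.1% looks like a simple product of step powers. That is correct only if the steps are independent, and here the seroprotection rate and the GMT are two summaries of the same hSBA titers in the same children.

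The stake is limited but real. Protocol 1.4 presents superiority of the serogroup C response over Nimenrix as what this trial adds to MET51, and 86.1% is the only stated power for completing that chain. The reader cannot tell which test, which dependence or which titer model it stands for.

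**Working it through.** **Inputs.** n = 202 per group (225 × 0.9 = 202.5); one-sided alpha 1.25%, z = 2.2414; rates 98% vs 88%; GMT ratio 1.5; SD 0.5. The tables give no unit for the SD; reading it as log10 reproduces their figures.

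**Reproducing the plan's figures**

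- Step 3: log10(1.5) = 0.1761; SE = 0.5 × √(2/202) = 0.0498; ratio 3.539. Normal power is Φ(3.539 − 2.241) = 90.3%; noncentral t gives 90.1%, as stated.
- Step 4, pooled normal approximation: SE under the null = √(2 × 0.93 × 0.07/202) = 0.02539; SE under the alternative = √((0.98 × 0.02 + 0.88 × 0.12)/202) = 0.02490. Power = Φ[(0.10 − 2.2414 × 0.02539)/0.02490] = Φ(1.731) = 95.8%, as stated.
- Chain: 0.901 × 0.999 × 0.999 = 89.9%, and 0.899 × 0.958 = 86.1%, as stated. The column is a product of step powers.

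**Step 4 with the planned test.** The Newcombe lower limit is d − √[(p1 − l1)² + (u2 − p2)²], where l1 and u2 are Wilson limits at z = 2.2414. Summing the binomial probabilities, at 98% and 88% with 202 per group, of all outcomes with a lower limit above 0 gives **97.2%**. For comparison, the unpooled normal formula gives 96.2% and a continuity-corrected one 93.7%.

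**Chain power without assuming independence.** For any dependence, the joint probability is at least the sum of the two powers minus 1, and at most the smaller of them.

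- Lower bound: 89.9% + 97.2% − 100% = **87.1%**.
- Upper bound: **90.1%** (step 3).
- Product under independence, planned test: 0.901 × 0.972 = 87.6%.
- Same bounds with the pooled 95.8%: 85.7% to 90.1%. The 86.1% is near the bottom of this range and falls below the range for the planned test.

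**Joint titer distributions that meet all the inputs** (40,000 simulated trials each, t-based GMT interval, Newcombe rate interval, continuous titers):

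- Normal log10 titers with SDs 0.414 (MenACYW) and 0.573 (Nimenrix). Root mean square SD is 0.5. Means lie above log10(8) by 0.414 × 2.054 = 0.850 and 0.573 × 1.175 = 0.674; the difference 0.176 is a ratio of 1.5. Chain power 88.8%.
- SD 0.5 in both arms, with 12% of the Nimenrix arm at titer 4 and the rest normal (mean 1.911, SD 0.280). This gives 98% vs 88% and a ratio of 1.5. Chain power 89.4%.

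**Sensitivity: log10-normal titers with a common SD of 0.5**

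- The rates imply a GMT ratio of 10^(0.5 × (2.054 − 1.175)) = 2.75. Chain power is then about 97%.
- GMT ratio 1.5 is a shift of 0.1761/0.5 = 0.352 SD. Keeping 88% for Nimenrix gives Φ(1.175 + 0.352) = 93.7% for MenACYW, with chain power about 38%. Keeping 98% for MenACYW gives Φ(2.054 − 0.352) = 95.6% for Nimenrix, with chain power about 14%.

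**The case against.** The case for leaving the tables alone is fair. A pooled normal approximation is a standard planning tool, and here it understates power. The product rule also errs on the low side. The primary objective is met at step 1 of either chain, powered above 99.9%; only the last step of one chain is touched, and step 3, GMT superiority, does not depend on how steps 3 and 4 are combined. All of this stands, and it is why the point is minor. It does not make the figures right: they are printed to a tenth of a percent, the column is labelled as overall power, and the planned interval is named in both documents.

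A reader might infer something stronger: that 98% vs 88%, a GMT ratio of 1.5 and SD 0.5 cannot all be true, and that real chain power could be 38% or less. The documents do not support this. It needs log-normal titers with the same SD in both arms, and neither is stated. The normal approximation is specified for an interval on means, not as a model of the lower tail at 1:8, and setting values below LLOQ to LLOQ/2 makes a cluster of low values plausible. The two distributions above meet every input. The 38% and 14% also depend on which rate is discarded, and both treat the GMT ratio of 1.5 as the truth. The tables source the rates and SDs to earlier toddler studies but name no source for that ratio. Protocol 1.2.1 reports an hSBA serogroup C ratio of 16.5 in naïve toddlers in MET51, and rates of 100% vs 89.5% in MET54. The 1.5 therefore looks like a cautious planning value.

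**Conclusion.** The point holds as a small error. Step-4 power for the planned test is 97.2%, not 95.8%, a difference of 1.4 points. Chain power is at least about 87.1% and at most about 90.1%, and about 89% in the joint distributions tried, so 86.1% is 1 to 4 points too low.

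The 97.2% needs only the stated rates, n and alpha. The bounds also take the stated step-3 power (89.9% to 90.1%) as given, and need no titer distribution. The 89% is illustrative, because other distributions can meet the same inputs. The 97%, 38% and 14% are conditional on a common-SD log-normal model; they show that the tables lack a stated assumption, and they are not replacement values. Nothing here questions the sample size, alpha split or tests.

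**What to change.** In the synopsis table and SAP Table 5.2 (and Protocol Table 12.1, listed in the contents but not visible in the copy reviewed, if it carries the same figures):

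1. Replace 95.8% with 97.2% and name the Newcombe interval as its basis.
2. Replace 86.1% with a chain power simulated from one stated joint titer distribution that meets the inputs (about 89%), or give the range 87% to 90% and say that it holds under any dependence between steps 3 and 4.
3. Add a note that, under log10-normal titers with a common SD of 0.5, 98% vs 88% and a GMT ratio of 1.5 do not agree. The rates imply a ratio of about 2.75 and chain power of about 97%; a ratio of 1.5 gives about 38% if 88% is kept, or about 14% if 98% is kept. Label these as conditional sensitivity figures.

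The cost is a short simulation and a few lines of text.
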